## Study Protocol and Analytic Plan

### Introduction

This study aims to examine the effects of 2 types of non-nutritive sweetener (NNS) warning labels on a sample of Chilean parents' product selection and perceptions. This document pre-specifies our planned analytic approach prior to data collection.

### Study Protocol

Participants will complete an online randomized experiment programmed in Qualtrics. After providing informed consent, participants will be randomly assigned to view 1 of 3 types of labels: a neutral control label, a text NNS warning label (i.e., Chilean NNS label), or an octagonal NNS warning label (i.e., Colombian NNS label).

First, participants will view their assigned label on four similar products (one unsweetened, one sweetened with sugar, one sweetened with NNS, and one sweetened with both sugar and NNS) displayed in random order. They will then complete a task in which they select one of the products to purchase for their child and identify which of the products contain NNS. During this task, in all experimental arms, products will also display Chile's current "high in sugar" and "high in calories" labels when applicable. This task will be repeated 3 times, each time with a different product category (i.e., fruit drinks, yogurts, breakfast cereals), with categories displayed in random order.

Next, participants will view their assigned label on two products containing NNS (i.e., flavored milk and cereal bar). For each product, participants will rate the perceived message effectiveness of the label, perceived product healthfulness, and perceived relative product healthfulness.

Lastly, after all product exposures, participants will rate their intentions to limit their child's NNS consumption.

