### Hypotheses

Correct identification of NNS-containing products (co-primary outcome): We predict that, compared to the control arm, correct identification of NNS-containing products will be higher for participants assigned to the Chilean NNS label arm or to the Colombian NNS label arm (H1).

Selection of NNS-sweetened product (co-primary outcome): We predict that, compared to the control arm, selection of the NNS-sweetened product will be lower for participants assigned to the Chilean NNS label arm or to the Colombian NNS label arm (H2).

Selection of unsweetened product (co-primary outcome): We predict that, compared to the control arm, selection of the unsweetened product will be higher for participants assigned to the Chilean NNS label arm or to the Colombian NNS label arm (H3).

Selection of sugar-sweetened product (secondary outcome): We predict that, compared to the control arm, selection of the sugar-sweetened product will not differ for participants assigned to the Chilean NNS label arm or to the Colombian NNS label arm (H4).

Perceived message effectiveness (secondary outcome): We predict that, compared to the control arm, the perceived message effectiveness (PME) of the labels will be higher for participants assigned to the Chilean NNS label arm or to the Colombian NNS label arm (H5).

Perceived product healthfulness (secondary outcome): We predict that, compared to the control arm, perceived product healthfulness will be lower for participants assigned to the Chilean NNS label arm or to the Colombian NNS label arm (H6).

Perceived relative product healthfulness (secondary outcome): We predict that, compared to the control arm, perceived relative product healthfulness will be lower for participants assigned to the Chilean NNS label arm or to the Colombian NNS label arm (H7).

Intentions to limit NNS consumption (secondary outcome): We predict that, compared to the control arm, intentions to limit their child's NNS consumption will be higher for participants assigned to the Chilean NNS label arm or to the Colombian NNS label arm (H8).

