## Main Analyses

We will use a two-sided critical alpha of 0.05 to conduct all statistical tests. All confidence intervals presented will use a 95% confidence level. Analyses of the primary and secondary outcomes will include all participants according to the trial arm to which they were randomized.

For all selection/identification tasks, we will code outcomes dichotomously. For correct identification of NNS-containing products, we will dichotomize the outcome to correct identification of NNS-containing products (coded as 1) vs. incorrect identification (coded as 0). Correct identification will be defined as having identified the two NNS-containing products in the set and no other products, while incorrect identification will be defined as any other scenario. For selection of NNS-sweetened product, we will dichotomize the outcome to selection of one of two NNS-sweetened products (coded as 1) vs. selection of either of the two non-NNS-sweetened products (coded as 0). For selection of unsweetened product, we will dichotomize the outcome to selection of the unsweetened product (coded as 1) vs. selection of any of the other three products (coded as 0). For selection of sugar-sweetened product outcome, we will dichotomize the outcome to selection of one of the two sugar-sweetened products (coded as 1) vs. selection of either of the other two non-sugar-sweetened products (coded as 0).

For dichotomous outcomes, we will first descriptively report unadjusted proportions in each experimental arm, including proportions for each product category and for all product categories simultaneously (e.g., whether the participant correctly identified the

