NNS-containing products in all three product categories). Next, to test H1-H4, we will use logistic mixed-effects regression models, treating the intercept as random to account for repeated measures within participants. Models will regress each outcome on indicator variables for the experimental arms, product categories, and their interactions. After model estimation, we will test the joint statistical significance of the interaction terms, and, if not significant, we will drop the interactions from the models. Regardless of the presence of the interaction terms in the final model, we will obtain the predicted probabilities of each outcome by experimental arm for each separate product category, which we will use to conduct a joint test of statistical significance of the differences in predicted probabilities across product categories. If such differences are jointly significant, we will report average differential effects (ADEs) of each type of NNS label (i.e., differences in predicted probabilities between each NNS label type and the control label) separately for each product category. Alternatively, if differences are not jointly significant, we will report ADEs of each type of NNS label across product categories.

For the PME outcome, we will verify that Cronbach's alpha is sufficient ( $>0.7$ ) and average each participant's scores across the three PME items. If Cronbach's alpha is not sufficient ( $<0.7$ ), we will treat each item as a separate construct instead. Next, for all continuous outcomes, we will descriptively report unadjusted means in each experimental arm, including means for each product category and averaged across all product categories. To test H5-H8, we will use linear mixed-effects regression models. Models will regress the outcomes on indicator variables for experimental arms, product category, and their interactions. After model estimation, we will test the joint statistical significance of the interaction terms. If the interactions are jointly significant, we will keep them in the models and report ADEs of each type of NNS label (i.e., differences in predicted means between each NNS label type and the control label) separately for each product category. Alternatively, if the interactions are not jointly significant, we will drop them from the models and report ADEs of each type of NNS label across product categories.

We will use complete case analysis to handle any missing data.

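### Two of each participant's three purchase selections follow an NNS identification question, so the planned effects for H2, H3 and H4 average unprompted and prompted label effects that the models cannot separate

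*Combined protocol and SAP*

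**What the plan says.** Study Protocol describes one task with two parts, in which participants "select one of the products to purchase for their child and identify which of the products contain NNS". It then states: "This task will be repeated 3 times, each time with a different product category". Categories appear in random order. The identification question therefore recurs in every category and is not held back until all selections have been made.

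The selections feed H2, which predicts that "selection of the NNS-sweetened product will be lower for participants assigned to the Chilean NNS label arm" (and likewise in the Colombian arm). They also feed H3 (unsweetened product) and H4 (sugar-sweetened product). Hypotheses lists H2 and H3 as co-primary and H4 as secondary.

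For H1 to H4, Main Analyses specifies logistic mixed models with a random intercept: "Models will regress each outcome on indicator variables for the experimental arms, product categories, and their interactions". Neither Main Analyses nor Exploratory Analyses mentions task position, an arm-by-position test or an analysis of the first task alone.

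**The concern.** Once participants have answered the identification question for one category, they know that NNS content is something the survey asks about. Their later selections are made with that cue.

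The cue need not act equally across arms, because the NNS labels display the attribute in question and the neutral control label does not. Parents in a label arm might attend more to the warning, which would enlarge the label effect. Parents in the control arm might start checking products for NNS, which would shrink it. Random category order spreads prompted selections evenly over fruit drinks, yogurts and cereals, but it leaves the average over categories a mixture.

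What is at stake is the interpretation of two of the three co-primary outcomes. A reader who wants to know how a label changes an ordinary purchase choice would receive an effect of which two-thirds comes from parents who had already been asked about NNS. The report would offer no way to see whether that mattered.

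**Working it through.** **Inputs.** Three tasks per participant, each with one selection and one identification (Study Protocol). There are 1,102 participants per arm and 3,306 in total, with 80% power and an effective size of 1,102 per arm (Sample Size and Power). The significance level is given by "We will use a two-sided critical alpha of 0.05 to conduct all statistical tests" (Main Analyses).

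**1. The plan's own figure.** The pooled-variance two-proportion formula, without continuity correction, is

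n = [1.960·√(2p̄(1−p̄)) + 0.842·√(p₁(1−p₁) + p₂(1−p₂))]² / (p₁−p₂)².

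With the printed sugar-sweetened rates 0.10 and 0.067, p̄ = 0.0835 and n = (0.767 + 0.329)² / 0.033² ≈ 1,102. This matches the plan. The same formula returns its other figures of 197, 82 and 435.

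**2. Share of selections after an NNS question.** If selection precedes identification within a task, the share is (3−1)/3 = 66.7%, which is 2 × 3,306 = 6,612 of 3 × 3,306 = 9,918 planned selections. The select-then-identify order is read from the wording. If identification came first within a task, the share would be 3 of 3.

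**3. What the average contains.** Let E be the label effect in the first task and E(1+k) the effect in the second and third. On the probability scale, the average over tasks is approximately

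[E + 2E(1+k)]/3 = E(1 + 2k/3).

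The documents give no value for k. The range below is assumed, for illustration only.

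| Assumed change in later tasks (k) | Average ÷ first-task effect |
|---|---|
| −50% | 0.67 |
| −25% | 0.83 |
| 0 | 1.00 |
| +25% | 1.17 |
| +50% | 1.33 |
| +100% | 1.67 |

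**4. Can the planned models separate the two parts?** No. Their terms are arm, category, arm by category and a random intercept. Because category order is random, position is balanced over category, and the arm-by-category terms carry no information on position.

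**5. What a first-category analysis could detect.** It uses one selection per participant, so 1,102 per arm.

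- From the plan's scenario tables, the H2 rates (NNS-sweetened plus NNS-and-sugar-sweetened) are 0.45 + 0.05 = 0.50 in control against 0.067 (90% scenario), or 0.30 + 0.20 = 0.50 against 0.267 (60% scenario). The H3 rates are 0.45 against 0.90, or 0.30 against 0.60. Power exceeds 99.9% in all four comparisons.
- For sugar-sweetened selection at 0.10 against 0.067, power is about 80%, as planned.
- Near a control rate of 45–50%, the smallest difference detectable with 80% power is about 6.0 points.
- Within one category there are about 1,102/3 ≈ 367 first selections per arm, and the detectable difference grows to about 10.3 points. Power for sugar-sweetened selection in the 90% scenario falls to about 37%.

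**The case against.** The strongest reply is that every arm receives the same question and arms are randomized. If the labels changed nothing, prompted or not, the question could not create a difference between arms. This stands. A reader might infer that the H2 and H3 estimates are biased, or that prompting could produce a spurious label effect. The documents do not support either reading. If a label worked only in prompted tasks, the averaged difference would still be a real effect of the label, in partly prompted parents. The documents also never state that the target is an unprompted choice. They do not state the opposite either, and a general aim about product selection will readily be read as ordinary choice.

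A second reply is that the plan's scenarios imply large differences: about 43 or 23 points for H2, and 45 or 30 for H3. Under those, a moderate change with prompting would alter the reported size but not whether an effect is found. This also stands, though they are planning scenarios and not expected results.

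A third reply is that asking all selections before any identification would not be free. H1, also co-primary, would be measured on a second viewing, after more label exposure, and this too could act differently by arm. This is correct and is why reordering is only an option here.

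Finally, first and later tasks also differ in practice, fatigue and accumulated label exposure, so a difference between them could not be attributed to the question alone. This limits what the added analysis can explain. It does not stop the first-category estimate from being free of any prior NNS question.

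**Conclusion.** The point holds as a limit on interpretation. On the order as written, two-thirds of the purchase selections follow an NNS question, and the main ADEs for H2, H3 and H4 are averages over one unprompted and two prompted tasks. The comparison between arms remains valid. The direction and size of any change with prompting cannot be derived from the documents, and the ratios of 0.67 to 1.67 shown above rest wholly on an assumed range. The conclusion depends on reading selection as preceding identification within a task. If the programmed survey does the reverse, no selection is unprompted and a first-category analysis would not supply one.

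**What to change.** 1. State explicitly that selection precedes identification within each task, and record each participant's category order.
2. Pre-specify a sensitivity analysis of H2, H3 and H4 using only each participant's first category. With one observation per person, this is an ordinary logistic regression on arm and category, with ADEs averaged over categories.
3. As support, add task position (first against later) and its interaction with arm to the main mixed models and report the joint test with estimates. A non-significant result should not be read as showing no carry-over.
4. In the report, describe the main ADEs as averaged over tasks of which two in three follow an NNS question.

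The cost is a few extra models. No new data are needed beyond the recorded order, and the 1,102 per arm already assumed as the effective size is kept. The downsides are wide intervals by category (about 367 first selections per arm in each) and a first-versus-later contrast that cannot isolate the question from practice, fatigue or label exposure.

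An optional alternative before launch is to show all three selection screens before any identification question. This costs three repeat displays and means accepting that H1 is then measured on a second viewing.

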### Hypotheses

Correct identification of NNS-containing products (co-primary outcome): We predict that, compared to the control arm, correct identification of NNS-containing products will be higher for participants assigned to the Chilean NNS label arm or to the Colombian NNS label arm (H1).

Selection of NNS-sweetened product (co-primary outcome): We predict that, compared to the control arm, selection of the NNS-sweetened product will be lower for participants assigned to the Chilean NNS label arm or to the Colombian NNS label arm (H2).

Selection of unsweetened product (co-primary outcome): We predict that, compared to the control arm, selection of the unsweetened product will be higher for participants assigned to the Chilean NNS label arm or to the Colombian NNS label arm (H3).

Selection of sugar-sweetened product (secondary outcome): We predict that, compared to the control arm, selection of the sugar-sweetened product will not differ for participants assigned to the Chilean NNS label arm or to the Colombian NNS label arm (H4).

Perceived message effectiveness (secondary outcome): We predict that, compared to the control arm, the perceived message effectiveness (PME) of the labels will be higher for participants assigned to the Chilean NNS label arm or to the Colombian NNS label arm (H5).

Perceived product healthfulness (secondary outcome): We predict that, compared to the control arm, perceived product healthfulness will be lower for participants assigned to the Chilean NNS label arm or to the Colombian NNS label arm (H6).

Perceived relative product healthfulness (secondary outcome): We predict that, compared to the control arm, perceived relative product healthfulness will be lower for participants assigned to the Chilean NNS label arm or to the Colombian NNS label arm (H7).

Intentions to limit NNS consumption (secondary outcome): We predict that, compared to the control arm, intentions to limit their child's NNS consumption will be higher for participants assigned to the Chilean NNS label arm or to the Colombian NNS label arm (H8).

## Main Analyses

We will use a two-sided critical alpha of 0.05 to conduct all statistical tests. All confidence intervals presented will use a 95% confidence level. Analyses of the primary and secondary outcomes will include all participants according to the trial arm to which they were randomized.

For all selection/identification tasks, we will code outcomes dichotomously. For correct identification of NNS-containing products, we will dichotomize the outcome to correct identification of NNS-containing products (coded as 1) vs. incorrect identification (coded as 0). Correct identification will be defined as having identified the two NNS-containing products in the set and no other products, while incorrect identification will be defined as any other scenario. For selection of NNS-sweetened product, we will dichotomize the outcome to selection of one of two NNS-sweetened products (coded as 1) vs. selection of either of the two non-NNS-sweetened products (coded as 0). For selection of unsweetened product, we will dichotomize the outcome to selection of the unsweetened product (coded as 1) vs. selection of any of the other three products (coded as 0). For selection of sugar-sweetened product outcome, we will dichotomize the outcome to selection of one of the two sugar-sweetened products (coded as 1) vs. selection of either of the other two non-sugar-sweetened products (coded as 0).

For dichotomous outcomes, we will first descriptively report unadjusted proportions in each experimental arm, including proportions for each product category and for all product categories simultaneously (e.g., whether the participant correctly identified the

NNS-containing products in all three product categories). Next, to test H1-H4, we will use logistic mixed-effects regression models, treating the intercept as random to account for repeated measures within participants. Models will regress each outcome on indicator variables for the experimental arms, product categories, and their interactions. After model estimation, we will test the joint statistical significance of the interaction terms, and, if not significant, we will drop the interactions from the models. Regardless of the presence of the interaction terms in the final model, we will obtain the predicted probabilities of each outcome by experimental arm for each separate product category, which we will use to conduct a joint test of statistical significance of the differences in predicted probabilities across product categories. If such differences are jointly significant, we will report average differential effects (ADEs) of each type of NNS label (i.e., differences in predicted probabilities between each NNS label type and the control label) separately for each product category. Alternatively, if differences are not jointly significant, we will report ADEs of each type of NNS label across product categories.

For the PME outcome, we will verify that Cronbach's alpha is sufficient ( $>0.7$ ) and average each participant's scores across the three PME items. If Cronbach's alpha is not sufficient ( $<0.7$ ), we will treat each item as a separate construct instead. Next, for all continuous outcomes, we will descriptively report unadjusted means in each experimental arm, including means for each product category and averaged across all product categories. To test H5-H8, we will use linear mixed-effects regression models. Models will regress the outcomes on indicator variables for experimental arms, product category, and their interactions. After model estimation, we will test the joint statistical significance of the interaction terms. If the interactions are jointly significant, we will keep them in the models and report ADEs of each type of NNS label (i.e., differences in predicted means between each NNS label type and the control label) separately for each product category. Alternatively, if the interactions are not jointly significant, we will drop them from the models and report ADEs of each type of NNS label across product categories.

We will use complete case analysis to handle any missing data.

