## **Exploratory Analyses**

Post estimation of each main analytic model, we will obtain exploratory comparisons between the outcomes in the two NNS label arms.

Additionally, we will examine whether gender and/or educational attainment moderates the effects of the NNS labels (compared to control) on the co-primary outcomes. If there are no significant differences in ADEs by product category in the main analyses, moderation analyses will use logistic mixed-effects models with random intercepts including indicator variables for experimental arms, the moderator, and their interactions. If, alternatively, there are significant differences in ADEs by product category in the main analyses, we will use separate regression models for each product category.

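### Naming gender and education in advance as covariates in the H1–H8 models could modestly tighten the ADEs; this is an optional gain on a valid unadjusted analysis

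*Combined protocol and SAP*

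**What the plan says.** For the dichotomous outcomes (H1–H4), Main Analyses states: "we will use logistic mixed-effects regression models, treating the intercept as random to account for repeated measures within participants". It then lists the terms: "Models will regress each outcome on indicator variables for the experimental arms, product categories, and their interactions". For the continuous outcomes (H5–H8) the list is the same: "Models will regress the outcomes on indicator variables for experimental arms, product category, and their interactions". The reported effect for the dichotomous outcomes is the ADE, defined as "differences in predicted probabilities between each NNS label type and the control label", given by product category or across categories depending on a joint test. Missing data are covered by one sentence: "We will use complete case analysis to handle any missing data".

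Gender and education appear only in Exploratory Analyses: "we will examine whether gender and/or educational attainment moderates the effects of the NNS labels (compared to control) on the co-primary outcomes". The documents do not say when the two questions are asked relative to label exposure, how they are coded, or how strongly they relate to any outcome. The Study Protocol section describes random assignment to three labels and mentions no stratification.

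**The concern.** Two participant characteristics are evidently collected, and a label shown in the same survey cannot change either trait, yet neither is used in the main comparisons. If education predicts, say, who correctly spots the sweetener-containing products, adjusting for it removes part of the between-participant variation from the label-versus-control contrast. It also accounts for chance differences in education between arms.

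The moderation models already carry the moderator's main effect, so the extra work is small. The plan describes itself in the Introduction as set before data collection, which is the right time to decide on covariates: adjustment chosen after the arms have been compared is open to selection. What is at stake is the width of the confidence intervals, not the validity of the estimates.

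**Working it through.** **The plan's own figure.** Sample Size and Power gives 1,102 per group for 0.10 versus 0.067 (two-sided 0.05, 80% power). The pooled-variance formula is n = [1.960·√(2·p̄(1−p̄)) + 0.842·√(p₁(1−p₁)+p₂(1−p₂))]² / (p₁−p₂)², with p̄ = 0.0835. The numerator is (0.767 + 0.329)² ≈ 1.200 and the denominator is 0.033² = 0.001089, so n = 1,102. The figure reproduces, without continuity correction. Total n is 3,306.

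**Inputs that the documents do not give (assumed).** Overall proportion p = 0.40; education split into equal halves; outcome difference d between halves of 10 or 20 points; correlation ρ between a participant's three responses of 0.2, 0.5 or 1. The value ρ = 1 matches the sizing assumption in Sample Size and Power that respondents choose alike in every category.

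**Formulas.**
- Variance of a participant's three-category mean: V = p(1−p)(1+2ρ)/3, with p(1−p) = 0.24.
- Variance explained by the two-level covariate: (d/2)², which is 0.0025 for 10 points and 0.01 for 20 points.
- Share removed: R = (d/2)²/V.
- Reduction in interval width: 1 − √(1−R).
- Equivalent extra participants: 3,306·R/(1−R).

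| ρ | V | d | R | Width reduction | Equivalent extra n |
|---|---|---|---|---|---|
| 1 | 0.240 | 10 | 1.0% | 0.5% | 35 |
| 1 | 0.240 | 20 | 4.2% | 2.1% | 144 |
| 0.5 | 0.160 | 10 | 1.6% | 0.8% | 52 |
| 0.5 | 0.160 | 20 | 6.3% | 3.2% | 220 |
| 0.2 | 0.112 | 10 | 2.2% | 1.1% | 75 |
| 0.2 | 0.112 | 20 | 8.9% | 4.6% | 324 |

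The ρ = 1 rows also apply when ADEs are reported by category, because each contrast then rests on one response per participant. With d = 0 the gain is zero.

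**Cross-check by simulation.** Two arms of 1,102, one binary response each, two binary covariates, and risk differences standardized from an ordinary logistic model. With the covariates explaining about 0.6%, 2.0% and 5.8% of the variance, the ratio of adjusted to unadjusted standard deviation was 0.999, 0.989 and 0.969. The mean risk difference did not change. The simulation had no random intercept, so it does not test that part of the planned model.

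**Effect on power.** At 1,102 per arm, a 50% versus 44% contrast (illustrative) has 80.6% power unadjusted. It has 81.0% if the covariates explain 1% of the variance and 82.6% if they explain 5%.

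**Chance imbalance.** For an equal split, the SD of the between-arm difference in the covariate is √(2·0.25/1,102) = 2.1 points. Multiplied by a 20-point outcome gap, that is about 0.4 points on the ADE.

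**The case against.** The strongest reply is that nothing here is wrong. An unadjusted, pre-specified comparison of randomized arms is valid, and no section promises adjustment. That stands.

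A reader might infer that precision is being given away free, that adjustment can only help, or that every ADE interval is wider than it need be. The documents do not support these readings, for five reasons.

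- Exploratory Analyses names gender and education as possible moderators of the label effect. That does not show that they predict the outcome, which is what a precision gain requires.
- The larger gains depend on a 20-point gap, and that gap cannot hold everywhere. In the 90% scenario, selection of either sweetener-containing product is 0.033 + 0.033 ≈ 0.067 in a label arm; equal halves 20 points apart would put one half at 0.067 − 0.10, below zero.
- On the plan's tables, power for two co-primary outcomes is already essentially 100% at 1,102 per arm. Sweetener-containing selection is 0.50 versus 0.067 or 0.50 versus 0.267, and unsweetened selection is 0.45 versus 0.90 or 0.30 versus 0.60. These are assumed rates, and none is given for correct identification.
- Adjustment has conditions. The plan does not say whether predicted probabilities are averaged over the random intercept or taken with it set to zero. In the second case, adding covariates changes the intercept variance and with it the ADE. Under the complete-case rule, missing covariate values would remove participants. If the questions come after exposure, non-response could differ by arm.
- Chance imbalance does not make the unadjusted result biased. The unadjusted interval already allows for it.

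What survives is a possible, modest gain at little cost.

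**Conclusion.** The main models are valid but leave out two characteristics that are evidently collected. Pre-specified adjustment could narrow ADE intervals by about 0.5% to 2.1% if responses are fully correlated or ADEs are reported by category, and by up to about 4.6% for a three-category average with correlation 0.2. It would gain nearly nothing if gender and education are not prognostic. These sizes rest on the assumed proportion of 0.40, equal education halves and 10- to 20-point gaps; none of these is in the documents. The continuous outcomes could not be sized, because no standard deviations are given. This is an optional efficiency improvement, not an error, and it is unlikely to change any conclusion for the two co-primary outcomes whose assumed contrasts are large.

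**What to change.** Add one pre-specified statement to Main Analyses that:

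- enters gender and educational attainment as fixed main effects in all H1–H8 models, with the coding and any merging of categories given;
- obtains the dichotomous-outcome ADEs by averaging predicted probabilities over the whole sample's covariate distribution and over the random intercept;
- has both questions asked before label exposure, or fills missing values by a rule that ignores arm, so that complete-case analysis drops nobody for them;
- keeps the unadjusted proportions and means already planned, reported alongside.

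The cost is slightly more specification work, possibly a change in question order, and logistic coefficients that become conditional on the covariates. With predictions averaged as above, the ADE keeps its meaning. No change to the sample size is needed.
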